Appendix 4 Mount Sinai Acute GVHD International Consortium (MAGIC) Acute GVHD Target Organ Staging

Table 1

GVHD Target Organ Staging

		Liver		
Stage	Skin (active erythema only)	(bilirubin)	Upper GI	Lower GI (stool output/day)
0	No active (erythematous) GVHD rash	< 2 mg/dl	No or intermittent nausea, vomiting or anorexia	Adult: < 500 ml/day or <3 episodes/day Child: < 10 ml/kg/day or <4 episodes/day
1	Maculopapular rash <25% BSA	23 mg/d1	Persistent nausea, vomiting or anorexia	Adult: 500–999 ml/day or 3–4 episodes/day Child: 10–19.9 ml/kg/day or 4–6 episodes/day
2	Maculopapular rash 25 – 50% BSA	3.1-6 mg/d1	-	Adult: 1000-1500 ml/day or 5-7 episodes/day Child: 20 - 30 ml/kg/day or 7-10 episodes/day
3	Maculopapular rash > 50% BSA	6.1–15 mg/dl	-	Adult: >1500 ml/day or >7 episodes/day Child: > 30 ml/kg/day or >10 episodes/day
4	Generalized erythroderma (>50% BSA) plus bullous formation and desquamation > 5% BSA	>15 mg/dl	-	Severe abdominal pain with or without ileus, or grossly bloody stool (regardless of stool volume).

Overall clinical grade (based upon most severe target organ involvement):

Grade 0: No stage 1-4 of any organ

Grade I: Stage 1-2 skin without liver, upper GI or lower GI involvement

Grade II: Stage 3 rash and/or stage 1 liver and/or stage 1 upper GI and/or stage 1 lower GI

Grade III: Stage 2-3 liver and/or stage 2-3 lower GI, with stage 0-3 skin and/or stage 0-1 upper GI

Grade IV: Stage 4 skin, liver or lower GI involvement, with stage 0-1 upper GI

Reference

Appendix 4: Mount Sinai Acute GVHD International Consortium (MAGIC) Acute GVHD Target Organ Staging

Percent Body Surface Area Calculation (Rule of Nines)

The percent body surface area (%BSA) of skin involvement is estimated assigning percentages to different body areas using the Rule of Nines (Moore et al. 2021) as shown in the figure below. The entire head is estimated as 9% (4.5% each for the anterior and posterior aspects). The entire trunk is estimated at 36% and can be divided into 18% for anterior components and 18% for the back. The anterior aspect of the trunk can further be divided into chest (9%) and abdomen (9%). The upper extremities total 18% and thus 9% for each upper extremity. Each upper extremity can further be divided into anterior (4.5%) and posterior (4.5%). The lower extremities are estimated at 36%, with 18% for each lower extremity. Again, each lower extremity can be further divided into 9% each for the anterior and posterior aspects. The groin is estimated at 1%.

References

- Wallace Rule of Nines for determining percent of burned body surface area. Contributed by OpenStax College, (Public Domain). In: StatPearls [resource on the Internet]. Treasure Island: StatPearls Publishing, January 2022.. Available from: https://www.ncbi.nlm.nih.gov/books/NBK537190/figure/article-38400.image.f1/.

Appendix 5 National Institutes of Health Chronic GVHD Diagnosis and Staging

	SCORE 0	SCORE 1	SCORE 2	SCORE 3
PERFORMANCE SCORE: KPS ECOG LPS	Asymptomatic and fully active (ECOG 0; KPS or LPS 100%)	Symptomatic, fully ambulatory, restricted only in physically strenuous activity (ECOG 1, KPS or LPS 80-90%)	Symptomatic, ambulatory, capal of self-care, >50% of waking hours o of bed (ECOG 2, KPS or LPS 60- 70%)	Symptomatic, bl limited self-care, 50% of waking bu hours in bed (ECOG 3-4, KPS or LPS <60%)
SKIN† SCORE % BSA GVHD features to be scored by BSA: Check all that apply: Maculopapular rash/eryth Lichen planus-like features Sclerotic features Papulosquamous lesions of ichthyosis	Mo BSA involved ema es	1-18% BSA	19-50% BSA	>50% BSA
Keratosis pilaris-like GV	HD			Check all that apply:
SCORE:	No sclerotic features		Superficial sclerotic features "not hidebound" (able to pinch)	Deep sclerotic features "Hidebound" (unable to pinch) Impaired mobility Ulceration
Other skin GVHD features (Check all that apply: Hyperpigmentation Hypopigmentation Poikiloderma Severe or generalized pro Hair involvement Nail involvement Abnormality present but of	(NOT scored by BSA) uritus explained entirely by no	on-GVHD documented	l cause (specify):	
MOUTH Lichen planus-like features present: Yes No Abnormality present but e	No symptoms explained entirely by ne	Mild symptoms with disease signs but not limiting oral intake significantly on-GVHD documented	Moderate symptoms with disease signs with partial limitation of oral intake d cause (specify):	Severe symptoms with disease signs on examination with major limitation of oral intake

Appendix 5:	National Institut	es of Health	Chronic GVHD	Diagnosis ar	nd Staging
-------------	-------------------	--------------	--------------	--------------	------------

	SCORE 0	SCORE 1	SCORE 2	SCORE 3
EYES Keratoconjunctivitis sicca (KCS) confirmed by ophthalmologist: Yes No Not examined Abnormality present bu	No symptoms	Mild dry eye symptoms not affecting ADL (requirement of lubricant eye drops $\leq 3 x$ per day)	Moderate dry eye symptoms partially affecting ADL (requiring lubricant eye drops > 3 x per day or punctal plugs), WITHOUT new vision impairment due to KCS	Severe dry eye symptoms significantly affecting ADL (special eyeware to relieve pain) OR unable to work because of ocular symptoms OR loss of vision due to KCS
GI Tract	No symptoms	Symptoms	Symptoms	Symptome associated
GI I ract Check all that apply: Esophageal web/ proximal stricture or ring Dysphagia Anorexia Nausea Vomiting Diarrhea Weight loss ≥5%* Failure to thrive Abnormality present but	No symptoms t explained entirely b	Symptoms without significant weight loss* (<5%)	Symptoms associated with mild to moderate weight loss* (5-15%) OR moderate diarrhea without significant interference with daily living	Symptoms associated with significant weight loss* >15%, requires nutritional supplement for most calorie needs OR esophageal dilation OR severe diarrhea with significant interference with daily living
LIVER	Normal total bilirubin and ALT or AP < 3 x ULN	Normal total bilirubin with ALT \geq 3 to 5 x ULN or AP > 3 x ULN	Elevated total bilirubin but ≤3 mg/dL or ALT > 5 ULN	Elevated total bilirubin > 3 mg/dL
Abnormality present bu	t explained entirely b	y non-GVHD documented	l cause (specify):	
Lungs**				
Symptom score :	No symptoms	Mild symptoms (shortness of breath after climbing one flight of steps)	Moderate symptoms (shortness of breath after walking on flat ground)	Severe symptoms (shortness of breath at rest; requiring 0 ₂)
Lung score: % FEV1	FEV1≥80%	FEV1 60-79%	FEV1 40-59%	FEV1 ≤39%
Not performed				

Abnormality present but explained entirely by non-GVHD documented cause (specify):

	SCORE 0	SCORE 1	SCORE 2	SCORE 3
JOINTS AND FASCIA P-ROM score (see below) Shoulder (1-7): Elbow (1-7): Wrist/finger (1-7): Ankle (1-4):	No symptoms	Mild tightness of arms or legs, normal or mild decreased range of motion (ROM) AND not affecting ADL	Tightness of arms or legs OR joint contractures, erythema thought due to fasciitis, moderate decrease ROM AND mild to moderate limitation of ADL	Contractures WITH significant decrease of ROM AND significant limitation of ADL (unable to tie shoes, button shirts, dress self etc.)
GENITAL TRACT (See Supplemental figure [‡] Not examined Currently sexually active Yes No	No signs)	Mild signs [‡] and females with or without discomfort on exam	Moderate signs [‡] and may have symptoms with discomfort on exam	Severe signs [‡] with or without symptoms
Abnormality present but	explained entire	ly by non-GVHD docume	ented cause (specify):	
Other indicators, clinical score to severity (0-3) ba	l features or com sed on functiona	plications related to ch l impact where applical	ronic GVHD (check all t ble none – 0,mild -1, mo	that apply and assign a derate -2, severe – 3)
Ascites (serositis)	Myast	thenia Gravis		
Pericardial Effusion	Periph	neral Neuropathy	Eosino	philia > 500/µl
Pleural Effusion(s)	Polyn	nyositis	Platelet	ts <100,000/µl
Nephrotic syndrome_	Weig	ht loss>5%* without GI s	symptoms Others	(specify):
Overall GVHD Severity (Opinion of the evaluator)	□ No GV	/HD 🛛 Mild	Moderate	Severe
Photographic Range of M	Iotion (P-ROM)			
	Shoulder		6 7(Normal)	
	Elbow		6 7 (Norma)	
	Wrist/finger		6 7 (Normal)	
	Ankle			

Appendix 5: National Institutes of Health Chronic GVHD Diagnosis and Staging

- * Skin scoring should use both percentage of BSA involved by disease signs and the cutaneous features scales. When a discrepancy exists between the percentage of total body surface (BSA) score and the skin feature score, OR if superficial sclerotic features are present (Score 2), but there is impaired mobility or ulceration (Score 3), the higher level should be used for the final skin scoring.
- * Weight loss within 3 months.
- **Lung scoring should be performed using both the symptoms and FEV1 scores whenever possible. FEV1 should be used in the final lung scoring where there is discrepancy between symptoms and FEV1 scores.
- Abbreviations: ECOG (Eastern Cooperative Oncology Group), KPS (Karnofsky Performance Status), LPS (Lansky Performance Status); BSA (body surface area); ADL (activities of daily living); LFTs (liver function tests); AP (alkaline phosphatase); ALT (alanine aminotransferase); ULN (normal upper limit).
- ‡ To be completed by specialist or trained medical providers (see Supplemental Figure).

Reference

GDC-8264—Genentech, Inc. 120/Protocol GA43861, Version 4

Appendix 6 Primary Disease Relapse or Progression Guidance

Primary disease relapse or progression is defined in Section 3.1.4.7. Additional guidance on assessment of relapse or progression is provided below.

For acute leukemia, chronic myeloid leukemia, and myelodysplastic syndrome (MDS), relapse is defined as meeting any of the following criteria:

- Reappearance of leukemia blast cells in the peripheral blood
- Greater than 5% blasts in the bone marrow not attributable to another cause (e.g., bone-marrow regeneration)
- For patients with MDS: appearance of previous or new dysplastic changes within the bone marrow, with or without falling donor chimerism
- Development of extramedullary leukemia or leukemic cells in the cerebral spinal fluid

For lymphoproliferative diseases, relapse or progression is defined as meeting all of the following criteria:

• Appearance of any new lesion more than 1.5 cm in any axis during or at the end of therapy, even if other lesions are decreasing in size

Increased fluoro-deoxyglucose (FDG) uptake in a previously unaffected site will be considered relapsed or progressive disease (PD) only after confirmation with other modalities. In patients with no prior history of pulmonary lymphoma, new lung nodules identified by computed tomography (CT) scan are mostly benign. Thus, a therapeutic decision should not be made solely on the basis of the positron emission tomography (PET) without histologic confirmation.

At least a 50% increase from nadir in the sum of the product diameters of any previously involved nodes, or in a single involved node, or the size of other lesions (e.g., splenic or hepatic nodules).

To be considered PD, a lymph node with a diameter of the short axis of less than 1.0 cm must increase by \geq 50% and to a size of 1.5 × 1.5 cm or more than 1.5 cm in the long axis.

- Lesion that is PET-positive if observed in a typical FDG-avid lymphoma or PET-positive before therapy, unless the lesion is too small to be detected with current PET systems (less than 1.5 cm in its long axis by CT)
- For patients with chronic lymphocytic leukemia (CLL) who present in complete remission prior to transplantation: in addition to the criteria above, reappearance of circulating malignant cells that are phenotypically characteristic of CLL

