3.1.4.7 Primary Disease Relapse or Progression

Primary disease relapse is defined as evidence of recurrent acute leukemia, myelodysplastic syndrome, or lymphoma per standard clinical, hematopathologic, and/or radiologic assessments (as indicated for primary disease). Primary disease progression applies to patients with lymphoproliferative diseases (lymphoma or chronic lymphocytic leukemia) not in remission prior to transplantation. The event is defined as increase in size of prior sites of disease or evidence of new sites of disease, documented or not by biopsy. See Appendix 6 for additional information.

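### Appendix 6 requires every listed criterion for lymphoproliferative relapse or progression, while Section 3.1.4.7, which it names as the definition, accepts new or growing disease sites as alternatives

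*Combined protocol and SAP*

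**What the plan says.** Appendix 6 opens by placing the definition elsewhere: "Primary disease relapse or progression is defined in Section 3.1.4.7. Additional guidance on assessment of relapse or progression is provided below".

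Section 3.1.4.7 has two rules. Relapse is "evidence of recurrent acute leukemia, myelodysplastic syndrome, or lymphoma per standard clinical, hematopathologic, and/or radiologic assessments". Progression applies to lymphoma or CLL not in remission before transplant: "The event is defined as increase in size of prior sites of disease or evidence of new sites of disease, documented or not by biopsy".

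For the same diseases, Appendix 6 then states: "For lymphoproliferative diseases, relapse or progression is defined as meeting all of the following criteria". The list contains:

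- a new lesion of more than 1.5 cm;
- growth of known disease: "At least a 50% increase from nadir in the sum of the product diameters of any previously involved nodes", with single nodes and other lesions treated likewise;
- a conditional PET criterion: "Lesion that is PET-positive if observed in a typical FDG-avid lymphoma or PET-positive before therapy", with the exception "unless the lesion is too small to be detected with current PET systems";
- for CLL in complete remission before transplant: "in addition to the criteria above, reappearance of circulating malignant cells that are phenotypically characteristic of CLL".

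The other disease groups in Appendix 6 need only one criterion: any for acute leukemia, chronic myeloid leukemia and myelodysplastic syndrome, and one or more for myeloma and for myeloproliferative neoplasms.

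Appendix 6 closes with two provisions that count relapse even when the criteria are not met: therapy given for persistent, progressive or relapsed malignancy, and death attributed to relapse.

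Relapse incidence and the FFS rate are exploratory efficacy endpoints (Section 6.6.2), summarized descriptively by treatment group. FFS requires, among other things, that the patient has not relapsed (Section 3.1.4.12).

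**The concern.** A site that works down the Appendix 6 list and a site that applies Section 3.1.4.7 can classify the same lymphoma patient differently. The appendix rule is the stricter one, so any error goes one way: fewer relapses and more failure-free patients.

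That direction matters. Section 1.2 says that a non-immunosuppressive treatment is desirable partly because it preserves the graft-versus-tumor response, and relapse incidence is the endpoint that speaks most directly to this. Section 6.1 says the dose will be chosen from all available safety, pharmacokinetic and efficacy data, with about 20 patients per cohort, so a single classification is visible in a cohort figure.

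**Working it through.** The plan gives no figure to reproduce here. The check sets the two texts side by side.

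**Case 1: a new lesion only.** A patient with lymphoma not in remission before transplant develops a confirmed new lesion above 1.5 cm, and known sites do not grow.
- Section 3.1.4.7: progression, because new sites suffice.
- Appendix 6: the new-lesion criterion is met and the growth criterion is not. Not all are met, so there is no event. A positive PET on the new lesion does not change this.

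**Case 2: growth only.** The same kind of patient has at least 50% growth from nadir in a known node and no new lesion.
- Section 3.1.4.7: progression, because growth of prior sites suffices.
- Appendix 6: the growth criterion is met and the new-lesion criterion is not, so there is no event.

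**Case 3: lymphoma in remission before transplant, recurring at one new site with pathological confirmation.**
- Section 3.1.4.7: relapse, on the relapse sentence.
- Appendix 6: its *all* rule covers relapse as well as progression, so this fails for the same reason as Case 1.

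**Case 4: CLL in complete remission before transplant, circulating malignant cells return, nothing else.** The CLL clause can be read as one more requirement on top of the rest (no event) or as a further way to qualify (event). The relapse sentence in Section 3.1.4.7 does not name CLL, so it does not settle the matter.

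**What the closing provisions of Appendix 6 recover.** In Cases 1 to 3, and in Case 4 on the stricter reading, the patient is counted once therapy for the malignancy is started or death is attributed to relapse. Still missed is a relapse that meets only some criteria, is untreated and is not the cause of death.

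**Evidence inside Appendix 6 about intent.** The new-lesion criterion applies even when other lesions shrink, a qualifier with little purpose if growth is also required. The accompanying notes discuss when a single finding (new FDG uptake, one enlarging node) may be taken as progression. Both fit a list of alternatives better than a joint requirement.

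**Effect on the endpoints.**
- Relapse incidence: each missed patient lowers the count by one. As a simple proportion in a cohort of 20, 1/20 = 5 percentage points.
- FFS: a missed relapse changes the result only if the patient is alive at the timepoint with no new line of aGVHD therapy and no chronic GVHD. Otherwise the patient has already failed.
- Number of such patients: it cannot be derived, because the documents give neither the mix of underlying diseases nor an expected relapse rate.

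**The case against.** The strongest reply is that the practical effect is small. The appendix calls itself additional guidance, so Section 3.1.4.7 arguably governs. Its progression rule covers only patients not in remission before transplant, and Section 4.1.2 excludes anyone with relapsed, progressing or persistent malignancy at entry, which narrows that group. In the relapse sentence, the choice offered is between types of assessment, not between lesion criteria. Section 3.1.4.7 has no size thresholds, so the two texts do not map onto each other exactly. Most relapses that matter clinically will be treated, and are then counted anyway.

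All of this limits the size of the problem. It does not remove the contradiction. Guidance that states its own definition, with *all* emphasized, will be followed by some assessors, and nothing says which text prevails. The relapse sentence is still permissive where the appendix is not.

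Three stronger readings are tempting and are not supported.

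- *Counting combinations of findings on which the two texts disagree, and treating that count as a measure of impact.* Such combinations are not patient frequencies. The count would also extend the progression rule to patients it does not cover and ignore the different thresholds.
- *Treating the layout of the growth criterion, or the relapse-date rule, as further defects.* The growth line has its own explanatory note and reads naturally as a separate criterion; a missing bullet is probably a conversion artefact. The date rule for treated disease joins detection and start of treatment, and is most naturally read as the date on which both are met.
- *Inferring that non-relapse mortality (NRM) is wrongly defined, because a patient who relapses and then dies of another cause can appear in both relapse incidence and Day 180 NRM.* Section 3.1.4.8 classifies deaths by attribution and so does say how that death is handled. The documents do not require the two endpoints to be mutually exclusive. A first-event definition is another coherent choice, not a correction.

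**Conclusion.** The conflict is real and the Appendix 6 rule is wrong as written: taken literally, it leaves uncounted a lymphoproliferative relapse or progression that Section 3.1.4.7 counts. The consequence is modest. It is confined to relapse incidence, which may be understated, and FFS, which may be overstated. Both are exploratory and descriptive; no primary or secondary endpoint and no formal test depends on this rule. The missed cases are mainly untreated relapses that are not the cause of death, in patients with lymphoproliferative disease, and their number cannot be estimated.

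The conclusion rests on two assumptions: that some assessors would apply the appendix list as worded, and that the growth line is a criterion in its own right. If it were not, *all* would still tie the new-lesion criterion to PET wherever PET applies. The Data Analysis Plan (DAP), to which Section 6 defers detailed methods, is not among the documents and may already address this.

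**What to change.** - Make Section 3.1.4.7 and Appendix 6 agree, so that one rule governs endpoint classification. Replace *all* in the lymphoproliferative list with wording under which new sites and growth of prior sites are alternatives, consistent with Section 3.1.4.7.
- Have the sponsor state what part PET plays (a criterion or a means of confirmation) and whether the CLL clause is a further requirement or a further way to qualify. The disease criteria themselves remain the sponsor's to set.
- Correct the myeloma text in Appendix 6, where relapse from complete response cites Section 3.1.4.1. That section defines complete response of aGVHD, not of myeloma.
- Optional: leave the NRM definition as it is and add to the DAP a supportive Day 180 analysis of death without prior relapse, with relapse as the competing event. One affected patient would be 1/20 = 5 points in a cohort of 20.

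The cost is wording only, with no new assessments or data. Any lymphoproliferative case already classified from the appendix list would need a second look. The downside for the sponsor is that reported relapse incidence may rise.

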Appendix 6: Primary Disease Relapse or Progression Guidance

For multiple myeloma, relapse or progression is defined as meeting any one or more of the following criteria:

• Direct indicators of increasing disease and/or end-organ dysfunction (i.e., hypercalcemia, renal failure, anemia, and bone disease) related to the underlying clonal plasma-cell proliferative disorder

> This criterion is not used in calculation of time to progression or progression-free survival but can be reported optionally or for use in clinical practice

• Development of new soft tissue plasmacytomas or bone lesions (osteoporotic fractures do not constitute progression)

Definite increase in the size of existing plasmacytomas or bone lesions, defined as a 50% (and \geq to 1 cm) increase as measured serially by the sum of the product diameters of the measurable lesion.

- Hypercalcemia (> 11 mg/dL)
- Decrease in hemoglobin of ≥2 g/dL not related to therapy or other non-myeloma-related conditions
- Rise in serum creatinine by 2 mg/dL or more from the start of the therapy and attributable to myeloma
- Hyperviscosity related to serum paraprotein

For the purposes of assessing relapse free survival, if patient is in complete response (CR; as defined in Section 3.1.4.1), relapse is defined as meeting any one or more of the following criteria:

- Reappearance of serum or urine M-protein by immunofixation or electrophoresis
- Development of \geq 5% plasma cells in the bone marrow
- Appearance of any other sign of progression (i.e., new plasmacytoma, lytic bone lesion, or hypercalcemia; see above).

For myeloproliferative neoplasms, relapse from CR is defined as meeting one or more of the following criteria:

- Reappearance of bone-marrow disease, including blasts, monocytic blast equivalents, or fibrosis
- New extramedullary disease, including new or reappearance of splenomegaly, hepatomegaly, skin lesions, etc.

Institution of any therapy to treat persistent, progressive or relapsed malignancy, including the withdrawal of immunosuppressive therapy or treatment of relapse with donor lymphocyte infusion, will be considered evidence of relapse/progression regardless of whether the criteria described above were met. The use of preemptive

GDC-8264—Genentech, Inc. 122/Protocol GA43861, Version 4 donor lymphocyte infusion is not considered as relapse. Relapse will also be considered to have occurred if the criteria described above were not met but the cause of death was attributed to relapse.

The date of relapse is the earlier of one of the following:

- Relapse criteria met
- Malignant disease that did not meet the specified relapse criteria was detected and treatment was initiated
- Death occurred and cause was reported as relapse

Non-malignant diseases will be considered to have a transplant status of persistent or active disease. Graft failures will be considered recurrence.

Appendix 7 Blood and Marrow Transplant Clinical Trials Network Severity Grading Table and Recurrence Interval Definitions

Type of Infection/ Severity Grade	Grade 1	Grade 2	Grade 3
Bacterial infections	Bacterial focus NOS requiring no more than 14 days of therapy for treatment (e.g., urinary tract infection)	Bacteremia (except CoNS) without severe sepsis ***	Bacteremia with deep organ involvement (e.g., with new or worsening pulmonary infiltrates; endocarditis)
	Coag Neg Staph (S. epi), Corynebacterium, or Proprioniobacterium bacteremia	Bacterial focus with persistent signs, symptoms or persistent positive cultures requiring greater than 14 days of therapy	Severe sepsis with bacteremia
	Cellulitis responding to initial therapy within 14 days	Cellulitis requiring a change in therapy d/t progression Localized or diffuse infections requiring incision with or without drain placement	Fasciitis requiring debridement
		Any pneumonia documented or presumed to be bacterial	Pneumonia requiring intubation
			Brain abscess or meningitis without bacteremia
	C. Difficile toxin positive stool with diarrhea < 1L without abdominal pain (child < 20 mL/kg)	C. Difficile toxin positive stool with diarrhea $\geq 1L$ (child $\geq 20 \text{ mL/kg}$) or with abdominal pain	C. Difficile toxin positive stool with toxic dilatation or renal insufficiency with/without diarrhea
Fungal infections	Superficial candida infection (e.g., oral	Candida esophagitis (biopsy proven).	Fungemia including Candidemia
	thrush, vaginal candidiasis)	Proven or probable fungal sinusistis confirmed radiologically without orbital, brain or bone involvement.	Proven or probable invasive fungal infections (e.g., Aspergillus, Mucor, Fusarium, Scedosporium).

Type of Infection/ Severity Grade	Grade 1	Grade 2	Grade 3
Fungal infections continued			Disseminated infections (defined as multifocal pneumonia, presence of urinary or blood antigen, and/or CNS involvement) with Histoplasmosis, Blastomycosis, Coccidiomycosis, or Cryptococcus. Pneumocystis jiroveci pneumonia (regardless of
Viral infections	Mucous HSV infection		PaO2 level)
	Dermatomal Zoster	VZV infection with 3 or more dermatomes	Severe VZV infection (coagulopathy or organ involvement)
	Asymptomatic CMV viremia untreated or a CMV viremia with viral load decline by at least 2/3 of the baseline value after 2 weeks of therapy	Clinically active CMV infection (e.g., symptoms, cytopenias) or CMV Viremia not decreasing by at least 2/3 of the baseline value after 2 weeks of therapy	CMV end-organ involvement (pneumonitis, enteritis, retinitis)
	EBV reactivation not treated with rituximab	EBV reactivation requiring institution of therapy with rituximab	EBV PTLD
	Adenoviral conjunctivitis asymptomatic viruria, asymptomatic stool shedding and viremia not requiring treatment	Adenoviral upper respiratory infection, viremia, or symptomatic viruria requiring treatment	Adenovirus with end- organ involvement (except conjunctivitis and upper respiratory tract)
	Asymptomatic HHV-6 viremia untreated or an HHV-6 viremia with a viral load decline by at least 0.5 log after 2 weeks of therapy	Clinically active HHV-6 infection (e.g., symptoms, cytopenias) or HHV-6 viremia without viral load decline 0.5 log after 2 weeks of therapy	
	BK viremia or viruria with cystitis not requiring intervention	BK viremia or viruia with clinical consequence requiring prolonged	

Appendix 7: Bone and Marrow Transplant Clinical Trials Network Severity Grading Table and Recurrence Interval Definitions

Type of Infection/ Severity Grade	Grade 1	Grade 2	Grade 3
Viral infections continued		therapy and/or surgical intervention Enterocolitis with enteric viruses	
		Symptomatic upper tract respiratory virus	Lower tract respiratory viruses
	Viremia (virus not otherwise specified) not requiring therapy	Any viremia (virus not otherwise specified) requiring therapy	
			Any viral encephalitis or meningitis
Parasitic infections			CNS or other organ toxoplasmosis
			Strongyloides hyperinfection
Nonmicrobiologic ally defined infections	Uncomplicated fever with negative cultures responding within 14 days Clinically documented infection not requiring inpatient management	Pneumonia or bronchopneumonia not requiring mechanical ventilation Typhlitis	Any acute pneumonia requiring mechanical ventilation Severe sepsis*** without an identified organism
			an identified organishi

Appendix 7: Bone and Marrow Transplant Clinical Trials Network Severity Grading Table and Recurrence Interval Definitions

*Concomitant or multimicrobial infections are graded according to the grade of the infection with the higher grade of severity.

**Therapy includes both PO and IV formulations

***Severe Sepsis

Adults:

Hypotension

-A systolic blood pressure of <90 mm Hg or a reduction of >40 mm hg from baseline in the absence of other causes for hypotension

Multiple Organ Dysfunction Syndrome

-2 or more of the following: Renal failure requiring dialysis, respiratory failure requiring bipap or intubation, heart failure requiring pressors, liver failure

Pediatrics:

-Pediatric SIRS definition and suspected or proven infection and cardiovascular dysfunction or ARDS or TWO or MORE other organ dysfunctions

Pediatric SIRS definition:

Two or more of the following, one of which must be abnormal temperature or leukocyte count

- 1) Core temperature >38.5C or < 36C
- 2) Tachycardia, otherwise unexplained persistent in absence of external stimulus, chronic drugs or painful stimuli. *or* bradycardia, in < 1 year old, otherwise unexplained persistent.
- 3) Tachypnea or mechanical ventilation for an acute process not related to underlying neuromuscular disease or general anesthesia
- 4) Leukocytosis or leukopenia for age (not secondary to chemotherapy) or >10% bands

Pediatric organ dysfunction criteria:

Cardiovavascular: despite administration of fluid bolus >40 ml/kg in 1 hour:

- Hypotension <5th percentile for age (or per Table 1)
- Pressors at any dose
- Two of the following:
 - \circ Capillary refill > 5 secs
 - Core to peripheral temperature $gap > 3^{\circ}C$
 - \circ Urine output < 0.5 mL/kg/hr
 - \circ Unexplained metabolic acidosis (Base deficit > 5.0 mEq/L)
 - \circ Blood lactate > 2 x ULN

Respiratory:

- ARDS or
- Intubated or
- >50% FiO2 to maintain SaO2 > 92%

Neurologic:

- Glasgow Coma Score $\leq 11 \text{ or}$
- Acute change in mental status with a decrease in GSC \geq 3 pts from abnormal baseline

Renal:

• Serum creatinine $\geq 2 \times ULN$ for age or 2-fold increase in baseline creatinine

Hepatic:

- Total bilirubin >4 mg/dL or
- ALT $\geq 2 \times ULN$ for age

GDC-8264—Genentech, Inc. 127/Protocol GA43861, Version 4

Appendix 7: Bone and Marrow Transplant Clinical Trials Network Severity Grading Table and Recurrence Interval Definitions

TADLE 1; FOUR AGE GROUPS RELEVANT TO HCT;						
				Leukocytosis /	Hypotension	
	Tachycardia	Bradycardia	Tachypnea	Leukopenia	Systolic BP	
